3.2.6. Colonoscopy and endoscopic mucosal resection (EMR)

Patients will have undergone colonoscopy prep as it is standard at each center, typically a polyethylene glycol lavage with 4–6 L until clear rectal fluid is evacuated. Periprocedural antithrombotic medications will be managed according to ASGE guidelines²³. All exams will be performed using high-definition colonoscopes with digital chromoendoscopy capability (e.g. Olympus 180 or 190 series or Pentax). Sedation will be provided as per standard of

care, typically moderate sedation using intravenous midazolam and a narcotic analgesic, or sedation per anesthesia if required.

Lesions will be identified using conventional colonoscopic views and further characterized using digital chromoendoscopy (e.g. narrow band imaging or i-Scan). Digital chromoendoscopy utilizes integrated electronically activated filters or electronic post-image processing techniques to enhance mucosal architecture and microvasculature. It allows detailed examination of polyp morphology and delineation of the lesion. Polyp characteristics will be recorded (see outcome measures).

Complete polyp resection during the first colonoscopy is intended. Endoscopic mucosal resection (EMR) using the strip biopsy method, as described by Karita et al²⁴, will be used for all resections.

This study will include the following standard steps (all considered standard of care):

1. The polyp will be submucosally injected, so that the lesion will lift and demarcate from the submucosal layer.
2. Polyp margins will be identified.
3. The polyp will be resected with electrocautery snare using one of two electrocautery settings (as per randomization).

Submucosal injectate: The submucosal injection creates a “cushion” between the mucosa and the muscularis propria. The idea is that mucosal lesions can be more safely removed. The applied injectate fluid will contain a lifting agent and a contrast agent. The lifting agent will be at the discretion of the endoscopist (e.g. NaCl or hydroxyethyl starch). The recommended preferred lifting agent will consist of a small amount of NaCl followed by an injection of a mixture of Hydroxyethyl starch (HES). In one recent study from Australia a HES equivalent (Gelufusin) had a similar rate of complications than NaCl, but a nonsignificant lower risk of adenoma recurrence (8 vs. 12 %)²⁵. Independent on the lifting agent used, it will be mixed with a contrast agent as typically used with EMR. The recommended preferred contrast agent will be Indigo carmine 0.4% at a ratio of approximately 100:1 (i.e. 0.1ml Indigo carmine and 10ml of HES). Indigo carmine is a contrast dye that has been routinely used for submucosal injection and for chromoendoscopy to enhance contrast between polyp and surrounding normal mucosa to delineate the margin of the polyp and to define the submucosal plane²⁶. Recent studies have used a modified EMR without using submucosal injection. Submucosal injection may make it more difficult to grasp polyp tissue of some polyps (e.g. flat sessile serrated adenomas/polyps). Similarly, immersing the polyp area in water (underwater EMR) may enhance engagement of the snare with the polyp and facilitate EMR²⁷. Endoscopists may not perform submucosal injection if they consider that it might make resection more difficult.

Snares: Various resection snares are available that differ in size, shape, and stiffness. During a polyp resection, different snares may be used dependent on size and morphology of polyp tissue. There are no data on the effect of snares on complications or on completeness of polyp resection. Preliminary assessment of resection practice showed that individual endoscopists at different study centers use different snares. The type of snare used is dependent on prior experience and availability at individual centers. We will therefore leave snare selection at the discretion of the endoscopist, document what snares were used, and examine whether snare selection had an effect on outcome.

Following resection, the endoscopist will confirm that the polyp appears to be completely resected macroscopically by detailed examination of the resection margin. Visible remaining polyp tissue should be resected or ablated (typically using argon plasma coagulation [APC]). Once resection is considered complete the mucosal defect will be either closed or not closed with clips, as determined per randomization protocol. After resection, the site will

be marked with spot injection to identify the polyp site at a future endoscopy (standard of care).

In some circumstances the endoscopist may consider it as clinically appropriate to place a clip, even if the patient was randomized to the non-clipping group. Such situations may include, but are not limited to placing a clip to control bleeding during the polyp resection. In these situations the endoscopist will be asked to document the reason for clip placement.

Following the procedure patients will be observed in recovery as per standard of care at each institution.

3.2.7. Follow-up procedures

The primary aim of the study is to assess whether clip closure of the mucosal defect after large polyp resection will reduce the risk of delayed bleeding complications. Secondary aims include to examine whether clip closure reduces the incidence of complications overall. Clip closure can therefore be considered effective if the risk of complications is reduced.

Follow-up:

- Patients will be contacted within 1-3 days to assess for any possible complications as per standard of care at each institution.
- Patients will be contacted after 30 days to inquire about possible adverse events.
- Per guideline patients with large polyps that are resected piecemeal should have a follow up colonoscopy within 3 to 6 months²⁸. The study will aim to schedule the recommended follow-up colonoscopies between 3 to 4 months.
- Assuming complete polyp resection a second follow-up colonoscopy will be scheduled one year following the first follow-up exam (within standard of care). Additional surveillance colonoscopies will be based on findings (third colonoscopy typically three years following the second colonoscopy). At follow-up the prior polypectomy site will be inspected for macroscopic residual polyp or recurrence and biopsies obtained from the site. We will collect information on colonoscopies and clinical course (i.e. need for surgery) up to five years after initial polyp resection.

3.2.8. Schedule of activities (Study table)

Schedule of activities is detailed in Figure 2, Appendix 4.

3.2.9. Study outcome evaluation

The *primary aim* of the study is to compare the incidence of delayed bleeding complications between patients after the resection of large ≥ 20 mm polyps who underwent clip application to those who did not.

The *secondary aim* is to compare the incidence of overall complications between patients after the resection of large ≥ 20 mm polyps with Endocut vs. low power coagulation.

3.2.9.1. Outcome measures

Primary Outcome Measure:

- Delayed bleeding complications [Time Frame: 30 days].

Assessment: Patient contact, if severe adverse event, review of medical records, to obtain details on complication, treatment and outcome.

Secondary Outcome Measures:

- Overall complications [Time Frame: 30 days]
Assessment: Patient contact, if severe adverse event, review of medical records, to obtain details on complication, treatment and outcome.
- Factors associated with complications [Time Frame: 30 days].
Assessment: Using patient and polyp characteristics, and procedural data, obtained at the time of study polyp resection.
- Complete polyp resection [Time Frame: 6 months]
Assessment: a) immediately after polyp resection, based on evaluation of the endoscopist. b) at first follow-up endoscopy, based on results of biopsies from the resection site.
- Polyp recurrence [Time Frame: 3 months to 5 years].
Assessment: at follow-up endoscopies after complete resection was achieved.
- Factors associated with incomplete resection or recurrence [Time Frame: 5 years].
Assessment: Using patient and polyp characteristics, and procedural data, obtained at the time of study polyp resection.

Procedures to assess safety of clip use

- Clip complications [Time Frame: 30 days].
Assessment: Patient contact, if severe adverse event, review of medical records, to obtain details on complication, treatment and outcome.

3.2.9.2. Study endpoints

Endpoints of primary analysis (Comparison between clip group versus no-clip group within 30 days of follow-up):

Primary endpoint:

- *Delayed bleeding complications:*

Delayed bleeding is a serious adverse event that is defined as a patient who left the endoscopy unit and subsequently had to return to any health care facility for evaluation of rectal bleeding AND who required either hospitalization, transfusion, a repeat colonoscopy or sigmoidoscopy for examination of the polypectomy site or control of bleeding, or surgery within 30 days after completion of the colonoscopy.

Secondary endpoint:

- *Complications overall:* Overall complications will be defined as an aggregate of all complications that occur at the time of the procedure (immediate complications) or during 30 days of follow-up. They include bleeding complications as defined above, perforation, postpolypectomy syndrome, and clinical events that require an ED visit, admission to the hospital, or additional testing or intervention.

Explorative:

- *Immediate and delayed complications:* Immediate complications are considered all complications at the time of polyp resection. They include bleeding that cannot be controlled by endoscopic intervention, perforation, or clinical events that require abortion of the procedure. Delayed complications are complications that occur following the completion of the colonoscopy within 30 days of the procedure.
- *Complete and partial clip closure:* Degree of closure of the resection defect will be categorized as completely closed, partially closed, and not closed. Complete closure is defined if opposing resection margins are drawn together by clips from one side to the other, with gaps of less than 1cm between the clips. A site is considered partially clipped if only a portion of the defect could be closed¹⁷.
- *Factors associated with complications:* Factors that may be associated with complications, including polyp size, location of the polyp in the colon (right, left, rectum), histology, polyp morphology, time required for resection.

Endpoints of secondary analysis (entire study cohort):

- *Complete polyp resection:* Rate of complete study polyp resection a) at the initial colonoscopy and b) at first follow-up endoscopy
- *Polyp recurrence:* Rate of recurrent polyp at the resection site after complete polyp resection.
- *Factors associated with incomplete resection or recurrence:* Factors that may be associated with incomplete resection include prior attempts of removal, use of adjunctive argon plasma coagulation for residual polyp removal, polyp size, location, and histology.

3.2.9.3. Data collection

We will collect the following data:

- Patient characteristics, including date of birth, gender, body mass index, ASA classification.
- General procedure details, including date of procedure, endoscopist, indication, and immediate complications.
- Polyp resection method, including prior biopsy, prior attempt of resection, perceived difficulty of positioning the endoscope, use of cap, submucosal injection, cautery current, type of snare, resection pieces, use of adjunct resection or cautery measures, number of clips placed, retrieval method, polypectomy time, clipping time, method of assessment of resection margins (e.g. NBI)
- Polyp characteristics, including polyp size, polyp site, histology polyp morphology (e.g. Paris classification), lifting sign, and supplemental methods.
- Follow-up data, including results of histopathology of the removed polyp, delayed complications.
- Follow-up procedure, including interval events (e.g. need for surgery), findings, presence of polyp/neoplasia at 4-6 months follow-up and within 5 years,
- Endoscopist characteristics include annual endoscopy procedure volume, years since training, average number of large polyp resections per year.
- Information on possible complications will be obtained at the time of the procedure, and identified based on the subjects' self-report at the post-procedure follow-up

phone call within 24-72 hours, at a phone call at least 30 days following the colonoscopy. Medical records will be reviewed for serious complications.

Image and video recording

Mandatory images will be taken during each polyp resection. These include an image before resection to verify the polyp size (adjacent snare with standardized size), and image after complete resection, and an image after clip closure if applicable. Further polyps that were not considered resectable will also be photographed.

Video recordings of all available EMR procedures will be collected from each participating endoscopist to understand not yet identified or possible non-measurable technical differences between endoscopists that might affect outcomes of interest.

All images and videos will be recorded without any patient identifier and stored at the coordinating site based on the patient, endoscopist, and center identification numbers.

3.2.10. Statistical analysis

3.2.10.1. Primary analysis: Comparison between clip group vs. no-clip group, 30 day follow-up)

Primary endpoint: Delayed bleeding complication.

We will assess the null hypothesis that clipping has no effect on delayed bleeding complications using a chi-square test to compare the two study arms (as randomized, intention-to-treat), or a Fisher's exact test if appropriate with a 5% significance level.

Secondary endpoint: Overall complications.

The secondary endpoint will be compared between the clip and no-clip arms using a chi-square test (or Fisher's exact test if appropriate) with a 5% significance level.

The primary endpoint (delayed bleeding complication) and secondary endpoint (overall complications) are planned to be used to support clip-labeling plans.

The main analyses of the primary and secondary endpoints will be done on a per subject basis. Additional analysis will be conducted at the unit per polyp. Clustering of polyps within patients (estimated to occur in approximately 5%) will be accounted for by using the method generalized estimating equations as well as mixed-effects-analysis with a random intercept for patient.

Subgroup Analyses: While the study is not powered to look at subgroups we will conduct exploratory analyses to determine if any difference in the clip and no-clip arms is modified by characteristics such as time of occurrence (immediate vs. delayed) and by etiology (bleeding, perforation, etc.). This examination will be descriptive because the study will unlikely be sufficiently powered for identifying differences as significant.

Explorative analysis of the effect of electrocautery setting: The comparison between the two electrocautery settings (low power coagulation vs. Endocut) will be explorative. Pilot data show that one third of participating endoscopists typically use low power coagulation and two thirds use Endocut. Acknowledging a possible effect of cautery on the incidence of complications there is a need to standardizing the cautery setting for the EMR procedure. Rather than using one cautery setting for all procedures, the cautery setting will be standardized by randomizing patients to one or the other setting. At the same time this randomization will allow an explorative analysis of the effect of cautery on complications. This

information, although descriptive, would provide valuable guidance to develop resection standards.

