3.2. Research Design and Methods

3.2.1. Design and patients

General study design: The study will be designed as a multicenter multi-endoscopist randomized trial.

A schematic diagram of the study design, procedures and stages is detailed in Figure 1, Appendix 3.

Study participants: Potential study participants will include patients with a colonic non-pedunculated polyp $\geq 20\text{mm}$ in size considered for endoscopic resection (see inclusion and exclusion criteria).

Anticipated number of research subjects (see also sample size calculation):

- Estimated number of participants for duration of entire study: Female: 470, Male: 550 (several sites are VA Medical Centers)
- Estimated total number at each site: ≥ 20

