3.2.5. Allocation to treatment (Randomization process)

Randomized will occur at the time of colonoscopy when a polyp has been identified as a study polyp using computer generated randomization. Patients will be randomized following a 2 x 2 factorial design to: (i) Endocut vs. low power coagulation after inspection of the polyp and decision to resect the polyp, and (i) clipping vs. no clipping of the mucosal defect after resection.

Patients will hence be randomized to one of four groups:

- A) Endocut and clipping,
- B) Endocut and no clipping,
- C) Low power coagulation and clipping, and
- D) Low power coagulation and no clipping.

Should a patient have more than one study polyp, all polyps will be resected in the same way (per patient randomization). The primary comparison will be between clip and no clip application. The comparison between cautery currents is secondary and exploratory.

Breaking the blind: The study is not blinded.

Treatment adherence/study compliance: The primary intervention (one-time clip placement) does not require adherence to the intervention. Participants will therefore not be excluded because of non-compliance.

The major outcome of interest will be assessed after 30 days following the intervention by a phone call. We expect that such short interval will allow an almost complete follow-up.

Secondary outcomes of interests include polyp recurrence during longer-term follow-up. We will collect data on all follow-up procedures that are performed as per standard of care (not as a study intervention).

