3.2.10.3. Interim Analysis

An interim analysis will be conducted when we have enrolled 50% of the targeted 1020 patients, and completed 30-day follow-up on them. We will conduct an efficacy and futility analyses. For efficacy of clipping we will stop the trial if the two-sided p-value is less than 0.01. This alpha spending means that at the final analysis, a two-sided p-value less than 0.044 will be considered significant. At the interim look we will calculate the conditional power and terminate the study for futility if the conditional power is less than 20%. If the study will be continued, we will not modify the sample size based on the results of the interim analysis.

Because higher risk lesions may be more likely to benefit from clip closure the study should not continue to enroll patients if such benefit is apparent before study completion. We will therefore perform an interim safety sub-analysis for two groups of patients:

- (a) Patients with study polyps >4cm, and
- (b) Patients who are on anticoagulation or resume anticoagulation within 14 days of the polyp resection.

We assume that either group will contribute 10 to 20% to the study. We plan to conduct this safety analysis for each of these subgroups after 60 patients have been enrolled into either of the two subgroups (i.e. after enrollment of 60 patients with a >4cm study polyp and separately after enrollment of 60 patients who resumed anticoagulation after polyp resection). For example, the safety analysis would detect the occurrence of 2 vs. 9 delayed bleeding complications in the non-clip vs. the clip group as a significant difference (RR 4.5, 95% CI 1.01, 19.96). The study should cease to enroll these patients if the interim safety analysis shows a significantly increased relative risk in delayed bleeding complications in the non-clip group compared to the clip-group (see also Section on Monitoring).

A second safety analysis for these two groups will be part of the interim analysis after enrollment of 50% of patients (see above). Similarly, should this analysis show a significant difference in delayed bleeding complications, these patients should not be further enrolled.

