3.2.10.4. Sample Size Determination

Our sample size calculation is based on the primary aim. We hypothesize that polyp resection with clip closure of the mucosal defect will reduce the incidence of delayed bleeding complications. Prior studies have reported an overall bleeding incidence between 2 and 24% (table 1). We consider an absolute difference of 5% in delayed bleeding incidence (e.g. 8% and 3%) as clinically important. Assuming a two-sided alpha of 0.05 and a power of 80%, the study will need to include a total of 730 subjects (365 subjects into each group) to show such difference as significant. We assume that for approximately 20% of patients clip

closure will not be considered possible. Therefore approximately 920 patients will need to be included. However, approximately 10% of potential study polyps of referred patients will not meet inclusion criteria (screen failures). We estimate therefore that we need to enroll (=consent) a total of 1,020 patients for 920 patients to undergo the study intervention.

Because the primary outcome measure (delayed bleeding) will be assessed after 30 days of the colonoscopy we do not expect any dropouts.

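### The primary test of clip versus no clip uses neither the randomised cautery arm nor the protocol's own risk factors, polyp size and anticoagulation; it is valid but gives up a little precision

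*Combined protocol and SAP*

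**What the plan says.** Section 3.2.10.1 compares the arms on the primary endpoint "using a chi-square test to compare the two study arms (as randomized, intention-to-treat". Fisher's test is the fallback, and significance is judged at 5%. The main analysis is per subject. The only dependence the plan models is between polyps in the same patient, and only in the additional per-polyp analysis.

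Cautery is the second randomised factor. Section 3.2.5 states: "Patients will be randomized following a 2 x 2 factorial design to" the two cautery settings and to clipping or no clipping. Section 3.2.10.1 accepts that cautery may affect complications but gives it only a separate exploratory comparison.

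On risk factors, section 3.1.1 says that severe complications become more frequent with polyp size, and lists anticoagulation among the factors that may affect complications. Section 3.2.10.3 sets up separate safety analyses for polyps above 4 cm and for anticoagulated patients, on the ground "Because higher risk lesions may be more likely to benefit from clip closure". It assumes each group makes up 10 to 20% of the study. Section 3.2.9.2 lists factors associated with complications as an exploratory endpoint. Logistic regression is named only for incomplete resection (section 3.2.10.2).

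The data items in section 3.2.9.3 include polyp size and cautery current. They do not name anticoagulation, although section 3.2.3 has it reviewed from the medical record at screening.

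**The concern.** The plan regards two baseline characteristics as important enough to have their own safety analyses, and randomises a third factor that it thinks may alter complications. None of the three is used in the comparison that decides the trial. When a baseline factor predicts the outcome, a test that accounts for it usually has somewhat more power for the same number of patients, and it removes the effect of any chance imbalance in that factor.

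Prespecification matters as well. Section 3.2.10.1 says the primary endpoint is meant to support labelling of the clip. If large polyps or anticoagulated patients fall unevenly between the arms by chance, an adjusted analysis will be asked for, and one chosen after the data are seen is open to dispute.

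**Working it through.** **1. The plan's own figure.** Inputs from section 3.2.10.4: 8% versus 3%, "Assuming a two-sided alpha of 0.05 and a power of 80"%, 365 per group. With z = 1.960 and 0.842 and mean rate 0.055:

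n = [1.960·√(2·0.055·0.945) + 0.842·√(0.08·0.92 + 0.03·0.97)]² / 0.05² = (0.632 + 0.270)² / 0.0025 ≈ 326.

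With continuity correction: n/4 · [1 + √(1 + 4/(n·0.05))]² = 81.5 · (1 + 1.116)² ≈ 365. The stated figure is reproduced. It was sized for the crude test.

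**2. Scenarios for the comparison.** The plan includes 920 patients, or 460 per arm. Two effect sizes are used:
- The planning rates, 8% versus 3%.
- A diluted effect. If the 20% of patients whose defect cannot be closed stay in the clip arm and bleed at 8%, that arm's rate is 0.8·3% + 0.2·8% = 4%.

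The normal-approximation power of the crude test is 91.5% and 72.5% at level 0.05, and 90.7% and 70.6% at the final level of 0.044.

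**3. Crude versus stratified test.** Simulation with 6,000 trials per scenario, N = 920, level 0.05 and simple allocation. The stratified test is Cochran-Mantel-Haenszel over large polyp × anticoagulation × cautery (eight strata). The following assumptions are not in the documents: the same odds ratio (OR) for each of the two risk factors, prevalence 15% at OR 2 and 20% at OR 3 and 5, cautery OR 1.5, 20 sites, and site SD 0.3 on the logit scale.

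| Rates | OR per risk factor | Crude | Stratified | Gain (points) |
|---|---|---|---|---|
| 8% vs 3% | 2 | 91.9% | 91.7% | −0.2 |
| 8% vs 3% | 3 | 92.8% | 93.1% | 0.3 |
| 8% vs 3% | 5 | 92.6% | 93.9% | 1.3 |
| 8% vs 4% | 2 | 72.4% | 72.8% | 0.4 |
| 8% vs 4% | 3 | 72.9% | 74.2% | 1.2 |
| 8% vs 4% | 5 | 73.4% | 76.3% | 2.9 |

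Gains are taken from unrounded power. Simulation error is about 0.4 to 0.6 points per figure, so the gain at OR 2 cannot be told from zero. A separate simulation at the final level of 0.044 gave the same range, about 0 to 3 points.

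**4. Validity.** With no clip effect (OR 3), the crude test rejected in 4.8% of trials and the stratified test in 4.9%.

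**5. What a chance imbalance could do.** Under simple allocation, the between-arm difference in a factor with prevalence p has SD √(4p(1−p)/N). At N = 920 this is 2.0 points for p = 10% and 2.6 points for p = 20%. The chance of a difference above 5 points is about 1% and 6% respectively. Suppose a 20% factor is imbalanced by 5 points and carries an assumed relative risk of 2. The bleeding rate without the factor is then 0.08/1.2 = 6.7%, and the arm difference shifts by 0.05·6.7% ≈ 0.3 points. At relative risk 3 the shift is 0.05·2·(0.08/1.4) ≈ 0.6 points. The target difference is 5 points.

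**6. Can the data support the model?** Expected events at 8% versus 4% are 460·0.08 + 460·0.04 ≈ 55, and at 8% versus 3% about 51. That is enough for a clip term and three covariates. A site with 20 patients would expect 20·5.5% = 1.1 events, too few for its own stratum to add much.

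**The case against.** The strongest defence is that an unadjusted intention-to-treat test is valid, transparent and the one the sample size was built on. Cautery is randomised, so it should be balanced across the clip arms by design. The power gain rests on odds ratios the documents do not give. The top of the range needs an odds ratio of 5 for both factors, and at 2 nothing is gained. All of that stands, and it is why the point is small. It does not argue against prespecifying the better test, which needs no more patients.

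A reader might infer more than this, but the documents do not support it:

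- *That allocation is an unrestricted draw.* Section 3.2.5 says only: "Randomized will occur at the time of colonoscopy when a polyp has been identified as a study polyp using computer generated randomization". No stratification or blocking is described, but silence does not show there is none. The imbalance figures in step 5 apply only if allocation is simple.
- *That some sites will have about 20 patients.* Section 3.2.1 gives "Estimated total number at each site: ≥ 20". That is a floor, and the number of sites is not stated.
- *That site is a named driver of bleeding.* It is not. The nearest text, in section 3.2.9.3, concerns possible differences in endoscopist technique.
- *That uneven splits undermine the 60-patient safety analyses.* A 36:24 split keeps 4·0.6·0.4 = 96% of the information of 30:30. Likewise, an uneven split at one site affects no planned analysis, because no within-site test is planned.

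**Conclusion.** The point holds as a modest loss of precision. The primary test omits one randomised factor and two baseline factors that the protocol itself singles out. At 920 patients the cost is about 0 to 3 percentage points of power under assumed odds ratios of 2 to 5, with little or no cost at 2. The range also depends on the assumed prevalences of 15 to 20%, within the plan's own 10 to 20%, and on the assumed cautery and site effects.

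The planned test is not biased and its type I error is held, so the trial's conclusion would not be invalid if nothing changed. The allocation method is a separate and lesser matter: it is under-described, and asking for it is a request for detail.

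**What to change.** Make the primary comparison of clip versus no clip a prespecified Mantel-Haenszel analysis, or a logistic model reporting a standardised risk difference so that the estimate stays on the scale of the 5-point target. Stratify by or adjust for:

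- cautery arm as randomised;
- polyp above 4 cm (yes/no);
- anticoagulant use known before allocation.

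Add anticoagulant use to the data items in section 3.2.9.3. Do not use resumption of anticoagulation within 14 days, because it occurs after allocation. Use the same statistic at the interim efficacy look and at the final analysis. Keep the crude chi-square or Fisher test as supportive. If site is included at all, enter it as a few pooled strata or a random intercept.

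As a secondary request, state the randomisation method in section 3.2.5, including any stratification factors and blocks. Any blocks within site should vary in size, because the trial is unblinded and fixed blocks would make allocations easier to predict.

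The cost is one data item, some analysis-plan wording and a slightly more complex analysis. No additional patients are needed.
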